9.4.2 Analysis of the Primary Efficacy Endpoint(s)

The primary endpoint, proportion of overall pain intensity responders is defined as a subject whose daily abdominal pain intensity averaged over the 4 weeks of Phase 3 (weeks 13 through 16) is 30% reduced compared to the daily abdominal pain intensity averaged over the 4 weeks of Phase 1 (weeks -4 through -1) (27). Responders will be compared between the GDH and comparator treatment groups using a Cochran-Mantel-Haenszel test adjusted for IBS subtype and gender. If the resulting p-value is less than 0.05 and the magnitude of the difference in pooled proportions is at least 10 percentage points, then it will be concluded that the primary endpoint has been met.

9.4.3 Analysis of the Secondary Efficacy Endpoint(s)

9.4.3.1 Abdominal Pain Intensity

Average abdominal pain intensity will be calculated as the average of the daily abdominal pain intensity scores recorded by each participant. Averages will be calculated for each week and for each 4-week assessment period (i.e., Phase 1 [Week -4 to -1,], Phase 3 [Week 13 – 16], etc.).

Average abdominal pain intensity at Week 13-16 will be statistically compared between GDH and MR using an ANOVA model adjusted for gender and IBS subtype. The least squares (LS) mean estimate of average abdominal pain intensity and LS mean difference and associated 95% CIs will be presented with corresponding p-value.

Additionally, change from baseline and at-assessment values of average abdominal pain intensity will be analyzed at all 4-week assessment time periods with a mixed effects repeated measures model (MMRM). The model will include treatment, time period, IBS subtype, gender, and treatment by time period interaction as fixed effects and participant as a random effect. The unstructured covariance matrix will be used to model the within-participant correlation. Using the ESTIMATE and LSMEANS statements within PROC MIXED, the model-based LS means and LS mean differences (GDH minus comparator) and associated 95% CIs for each time period and overall will be estimated.

Average abdominal pain intensity will be summarized descriptively by treatment and time period.

Additionally, overall pain intensity response at all 4-week assessment time periods will be analyzed with a random effects generalized estimating equations (GEE) with a logit link. The model will include treatment, time period, IBS subtype, gender, and treatment by time period interaction as fixed effects and subject as a random effect. The unstructured covariance matrix will be used to model the within-subject correlation. Using the ESTIMATE and LSMEANS statements within PROC GLIMMIX, the model-based responder rates and odds ratio (GDH relative to comparator) and associated 95% CIs for each time period and overall will be estimated.

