Statistical Analyses:	
Primary Endpoints The primary endpoint, proportion of overall pain intensity responders, will be compared between the GDH and MR treatment groups using a Cochran-Mantel-Haenszel test adjusted for IBS subtype and gender. Safety will be summarized using descriptive statistics.
 
Secondary Endpoints Average abdominal pain frequency and average abdominal pain intensity at Week 13-16 will be statistically compared between GDH and MR using an ANOVA model adjusted for gender and IBS subtype. The least squares (LS) mean estimate of average abdominal pain intensity and LS mean difference and associated 95% CIs will be presented with corresponding p-value.
 
Additionally, change from baseline and at-assessment values of average abdominal pain frequency and average abdominal pain intensity will be analyzed at all 4-week assessment time periods with a mixed effects repeated measures model (MMRM).
 
Average abdominal pain frequency and average abdominal pain intensity will be summarized descriptively by treatment and time period.
 
Stool consistency response will be analyzed with methods similar to those used to assess the primary endpoint, as described in the Statistical Analysis Plan.
 
IBS-QOL, WPAI, PHQ-4 will be analyzed with MMRM and summarized descriptively by treatment and week.
 
See the Statistical Analysis Plan for details regarding all analyses.
 
Sample Size Justification In this study, a total of approximately 380 subjects will be randomized in a 1:1 ratio to GDH or comparator to ensure that at least 300 subjects complete their Week 13-16 assessment (Phase 3) for analysis. Three hundred (300) Phase 3 completers will provide at least 90% power to detect an 18 percentage point difference in response rates between the GDH and comparator treatment groups at the 5% significance level. The study was powered assuming that the comparator treatment group is expected to

------------------------------	--

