9.4 Statistical Analyses

9.4.1 General Approach

The SAS System, Version 9.4 (or higher), will be used for all analyses, unless otherwise specified. Continuous variables (e.g., age) will be summarized using the number of observations (n), mean, standard deviation (SD), median, minimum, and maximum. Categorical variables (e.g., sex, race) will be summarized using the number of observations (n) and percentage in each category.

All data used in analyses and/or collected during the study will be provided in listings. Subjects withdrawn prior to end of Phase 3 (Weeks 13-16) assessment period will be considered as prematurely withdrawn. All available data for subjects who prematurely withdraw from the study will be included in all analyses. All 4-week assessment periods in MMRM and GEE models will include: Phase 1 (weeks minus 4 through minus 1), Phase 2 weeks 1-4, Phase 2 weeks 5-8, Phase 2 weeks 9-12, Phase 3 (weeks 13-16), LTE Period 1 (weeks 35 through 38), and LTE period 2 (weeks 61 through 64). At timepoints during the study that require 4 weeks of daily IBS symptom and pain assessment, at least 50% of the required assessments must be collected to be able to derive the average daily abdominal pain intensity and like endpoints. Study withdrawals, reasons for withdrawal, and missing assessment collections will be summarized.

Analyses of treatment will be performed using two different approaches to account for missing data during the treatment phase:

1. At-assessment Analysis: Missing values at post-baseline assessments will not be replaced and will be regarded as missing in analyses.
2. Multiple Imputation: Missing values at post-baseline assessments will be imputed using the multiple imputation method.

Additional details of the statistical methods are provided in the SAP.

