9.4.3.2 Average Abdominal Pain Frequency

Average abdominal pain frequency is defined as the average number of days during the 4-week assessment period in which the subjects recorded a 1 or greater on the daily pain severity measurement. Only days during which an assessment is recorded will be included in the calculation of average abdominal pain frequency.

Average abdominal pain frequency at Week 13-16 will be statistically compared between GDH and comparator using an ANOVA model adjusted for gender and IBS subtype. The least squares (LS) mean estimate of average abdominal pain frequency and LS mean difference and associated 95% CIs will be presented with corresponding p-value.

Additionally, change from baseline and at-assessment values of average abdominal pain frequency will be analyzed at all 4-week assessment time periods with a mixed effects repeated measures model (MMRM). The model will include treatment, time period, IBS subtype, gender, and treatment by time period interaction as fixed effects and subject as a random effect. The unstructured covariance matrix will be used to model the within-subject correlation. Using the ESTIMATE and LSMEANS statements within PROC MIXED, the model-based LS means and LS mean differences (GDH minus comparator) and associated 95% CIs for each time period and overall will be estimated.

Average abdominal pain frequency will be summarized descriptively by treatment and time period.

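### The Week 13-16 pain ANOVAs and the accompanying MMRMs leave out the Phase 1 average as a covariate, which costs precision that could be had without new data

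*Combined protocol and SAP*

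**What the plan says.** Section 4.2.2 lists mean change from Phase 1 to Phase 3 in pain intensity and pain frequency among the secondary endpoints. Three places give the Week 13-16 comparison:

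- Section 9.4.3.1: average pain intensity "will be statistically compared between GDH and MR using an ANOVA model adjusted for gender and IBS subtype".
- Section 9.4.3.2: average pain frequency "will be statistically compared between GDH and comparator using an ANOVA model adjusted for gender and IBS subtype".
- Synopsis: "Average abdominal pain frequency and average abdominal pain intensity at Week 13-16 will be statistically compared between GDH and MR using an ANOVA model", with the same two adjustment factors.

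This ANOVA comes first, and it is the only pain-mean model promised a p-value: "LS mean difference and associated 95% CIs will be presented with corresponding p-value".

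An MMRM is then added, on two scales: "change from baseline and at-assessment values of average abdominal pain intensity will be analyzed at all 4-week assessment time periods". Its terms are listed in full: "The model will include treatment, time period, IBS subtype, gender, and treatment by time period interaction as fixed effects", with the participant as a random effect and an unstructured covariance. The pain-frequency MMRM has the same list. Phase 1 enters only as a response period. Section 9.4.1 states: "All 4-week assessment periods in MMRM and GEE models will include: Phase 1 (weeks minus 4 through minus 1", and then names six post-baseline periods. It also says: "All available data for subjects who prematurely withdraw from the study will be included in all analyses".

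The covariate exists. Section 6.2 requires pain scores on 70% or more of the 28 run-in days, and section 9.4.1 needs only half the entries to derive a 4-week average. Pain frequency comes from the same scores (section 8.4.2).

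**The concern.** The outcome is a 4-week mean of a daily score, and the same mean is measured before randomisation. The pre-treatment value of the outcome is often its strongest single predictor, yet the plan adjusts for gender and subtype and not for this. Confidence intervals for the secondary pain means are then wider than they need be.

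The plan also gives a value analysis and a change analysis without saying which one answers the endpoint in section 4.2.2. Without baseline adjustment, the two answers differ by the chance baseline imbalance between arms.

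A separate specification fault lies in the same text. Change from baseline at Phase 1 is zero for every subject. That period has zero variance, so an unstructured covariance over all seven periods is singular.

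**Working it through.** **The plan's own figure.** The only power statement is for the primary responder endpoint (section 9.2): 44% against 26%, 150 per arm, two-sided 5%. The pooled-variance formula gives SE0 = sqrt(2 x 0.35 x 0.65/150) = 0.0551 and SE1 = sqrt((0.44 x 0.56 + 0.26 x 0.74)/150) = 0.0541. Power is Phi((0.18 - 1.96 x 0.0551)/0.0541) = 90.9%, as stated. This point does not affect it. The documents give no SD, correlation or power for the pain means.

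**Assumed inputs.** rho, the correlation of the Phase 1 and Week 13-16 averages: 0.3, 0.5, 0.7. k, the ratio of Phase 1 SD to Week 13-16 SD: 1, or 0.75 because the entry floor of average pain 3 or more may narrow the baseline spread.

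**Complete data.** Variance of the treatment difference relative to the ANOVA: change score 1 + k^2 - 2 x rho x k; ANCOVA 1 - rho^2.

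| | rho 0.3 | rho 0.5 | rho 0.7 |
|---|---|---|---|
| ANOVA | 1.00 | 1.00 | 1.00 |
| Change score, k = 1 | 1.40 | 1.00 | 0.60 |
| Change score, k = 0.75 | 1.113 | 0.813 | 0.513 |
| ANCOVA | 0.91 | 0.75 | 0.51 |
| Gain over the better of ANOVA and change, k = 1 | 9% | 25% | 15% |
| The same, k = 0.75 | 9% | 8% | under 1% |

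A simulation of 4000 runs with 150 per arm and k = 1 agreed: ANCOVA 0.91, 0.77, 0.51.

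**Does Phase 1 as a response period already supply the adjustment?** No. With a free treatment difference at Phase 1 and complete data, the generalised least squares variance of the value contrast at Week 13-16 is 1.00 at all three correlations. It drops to 0.91, 0.75 and 0.51 only if the arms are constrained equal at Phase 1.

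**With dropout.** Section 6.5 allows up to 20%: 190 per arm randomised, 152 observed at Week 13-16. Post-baseline correlations of 0.6, 0.7 and 0.8 are assumed alongside the three rho values. Variances are relative to the completers' ANOVA.

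If only Week 13-16 onward is missing, the dropouts still supply Phase 1 and three treatment periods. These predict the Week 13-16 value with R^2 = 0.494, 0.618, 0.745. The value MMRM has variance 1 - 0.2 x R^2, and the baseline-adjusted MMRM has (1 - rho^2) - 0.2 x (R^2 - rho^2).

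| | rho 0.3 | rho 0.5 | rho 0.7 |
|---|---|---|---|
| Value MMRM (planned) | 0.901 | 0.876 | 0.851 |
| Change MMRM (planned, Phase 1 removed), k = 1 | 1.224 | 0.878 | 0.531 |
| Change MMRM, k = 0.75 | 0.992 | 0.727 | 0.461 |
| Baseline-adjusted MMRM | 0.829 | 0.676 | 0.459 |
| Gain over best planned, k = 1 | 8.0% | 22.8% | 13.6% |
| Gain over best planned, k = 0.75 | 8.0% | 6.9% | 0.4% |

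If all dropout comes before any post-baseline data, the value MMRM has 1 - 0.2 x rho^2 = 0.982, 0.950, 0.902. The gains are then 7.3%, 21.1%, 15.0% (k = 0.75: 7.3%, 7.7%, 0.5%). Dropout spread evenly over four windows gives 7.8%, 22.3%, 13.9% (k = 0.75: 7.8%, 7.1%, 0.4%).

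A completers-only ANCOVA does not always win. At rho 0.7, k = 0.75, with only Week 13-16 onward missing, its 0.51 is worse than the planned change MMRM at 0.461. The covariate therefore belongs in both models.

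**Chance imbalance.** With k = 1, an imbalance d moves the ANOVA estimate by about rho x d and the change estimate by about -(1 - rho) x d; the gap is d. At 150 per arm, SE(d) = sqrt(2/150) = 0.115 SD, expected |d| = 0.092 SD and P(|d| > 0.2 SD) = 8%. The ANOVA 95% half-width is 1.96 x 0.115 = 0.226 SD.

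**Phase 1 as a change response.** The seven-period covariance of change has rank 6, with variance zero at Phase 1. On the value scale, an overall contrast averaged over all seven periods would shrink a constant treatment effect to 6/7.

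**The case against.** The unadjusted analyses are valid, the endpoints are secondary with no stated success rule, and the size of the loss rests wholly on assumed correlations. The plan already has a change-from-baseline MMRM, against which the gain can almost vanish. Pain frequency is a bounded count of days in subjects selected for pain, so its correlation could be lower than 0.3; at 0.1 or 0.2 the complete-data gain, rho^2, is only 1% or 4%. Section 9 promises a separate SAP that may add terms.

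Much of this stands as a limit on size. None of it is a reason to leave the covariate out: in the scenarios computed, the adjusted MMRM was never less precise than the alternatives. A later SAP could add detail, but the term lists here are explicit and should be right in themselves.

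Two further points are fair. First, sensitivity to chance imbalance is not a cost on top of lost precision. It is the same variance seen after the baseline is known, and the interval already allows for it; only rho x d reaches the ANOVA. What remains is that the two planned scales can disagree by d.

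Second, unbiasedness needs its condition. Randomisation secures it for complete data, but not where dropout depends on baseline differently by arm. In an illustrative simulation (190 per arm, logit of dropout -1.5 plus or minus 0.6 per baseline SD, opposite signs by arm, about 20% lost), the completers' ANOVA was biased by 0.07, 0.11 and 0.15 SD at rho 0.3, 0.5 and 0.7, and ANCOVA by about zero. The planned multiple imputation was not evaluated. This objection strengthens the case for the covariate.

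**Conclusion.** The point holds. The pain ANOVAs and MMRMs omit an available baseline covariate, and listing Phase 1 as a response period does not replace it. Against the ANOVA, the variance saving is rho^2: 9% to 49% over the assumed range. Against the best planned model with 20% dropout it is 7% to 23% with equal SDs. With the Phase 1 SD at 0.75 of the later SD it is about 7-8% at rho 0.3 and 0.5, and under 1% at 0.7. All these sizes depend on assumed correlations and SD ratios.

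The primary Cochran-Mantel-Haenszel test and the sample size are unaffected. This is a change that should be made, not an error that invalidates the trial. The zero-variance Phase 1 change response needs correcting whatever correlation is assumed.

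**What to change.** - In sections 9.4.3.1 and 9.4.3.2 and the synopsis, replace the Week 13-16 ANOVA with an ANCOVA on treatment, gender, IBS subtype and the Phase 1 average of the same measure.
- Add that average and its interaction with period to both pain MMRMs, and limit the response to the six post-baseline periods. Under three assumed decaying correlation patterns, a single common slope inflated variance by 0.4-1.9% at Week 13-16 but by 4.6-14.5% at weeks 61-64, so the interaction matters mainly for the extension.
- With the Phase 1 average in the model, the value and change versions give the same treatment difference, so report one.
- Name one model as the main analysis of the Phase 1 to Phase 3 mean change and label the rest supportive. The adjusted MMRM's Week 13-16 contrast is the natural choice.
- The same covariate can go into the stool, IBS-QOL and WPAI models (sections 9.4.3.3 to 9.4.3.6). Remove the baseline time point from every change response: section 9.4.3.5 lists the Baseline visit for IBS-QOL, and WPAI follows it.

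The cost is one term in each ANCOVA, six slopes in each pain MMRM, a shorter period list and one sentence naming the main model, all to be settled before unblinding. No new data are needed, and no correctly randomised subject leaves the pain analyses for want of a baseline. Change models already require the baseline value. A missing-baseline rule is needed only where at-assessment values of stool frequency, IBS-QOL or WPAI are modelled, since the 70% diary rule covers pain scores alone and section 2.3 merely asks subjects to complete the baseline surveys.

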9.4.3.2 Average Abdominal Pain Frequency

Average abdominal pain frequency is defined as the average number of days during the 4-week assessment period in which the subjects recorded a 1 or greater on the daily pain severity measurement. Only days during which an assessment is recorded will be included in the calculation of average abdominal pain frequency.

Average abdominal pain frequency at Week 13-16 will be statistically compared between GDH and comparator using an ANOVA model adjusted for gender and IBS subtype. The least squares (LS) mean estimate of average abdominal pain frequency and LS mean difference and associated 95% CIs will be presented with corresponding p-value.

Additionally, change from baseline and at-assessment values of average abdominal pain frequency will be analyzed at all 4-week assessment time periods with a mixed effects repeated measures model (MMRM). The model will include treatment, time period, IBS subtype, gender, and treatment by time period interaction as fixed effects and subject as a random effect. The unstructured covariance matrix will be used to model the within-subject correlation. Using the ESTIMATE and LSMEANS statements within PROC MIXED, the model-based LS means and LS mean differences (GDH minus comparator) and associated 95% CIs for each time period and overall will be estimated.

Average abdominal pain frequency will be summarized descriptively by treatment and time period.

9.4.3.3 Stool Consistency

Stool Consistency will be calculated using the BSFS. The BSFS is recorded at approximately the same time each day. Subjects will be asked for the number of bowel movements in the previous

24 hours. Subjects will use the BSFS to score the worst stool in the preceding 24 hour period. Extreme stool consistency is defined as 1, 2, 6, or 7 on the BSFS, while BSFS scores of 3,4 and 5 are considered within the normal range. The BSFS scores will be grouped as 1,2 (Group 1), 3,4,5 (Group 2) and 6,7 (Group 3). For participants in the IBS-D and IBS-M subtypes, a stool consistency response is defined as having a greater than or equal to 50% reduction from baseline (Phase 1) in the number of days with a BSFS score of 6 or 7. Stool consistency response for the IBS-D and IBS-M subtypes will be analyzed with methods similar to those used to assess the primary endpoint described in [Section 10.4.2](#).

Additionally, change from baseline in the percentage of days with a BSFS score in Group 2 will be analyzed at all 4-week assessment time periods with a mixed effects repeated measures model (MMRM). The model will include treatment, time period, IBS subtype, gender, and treatment by time period interaction as fixed effects and subject as a random effect. The unstructured covariance matrix will be used to model the within-subject correlation. Using the ESTIMATE and LSMEANS statements within PROC MIXED, the model-based LS means and LS mean differences (GDH minus comparator) and associated 95% CIs for each time period and overall will be estimated.

The percentage of the number of days with a BSFS score in each BSFS group will be summarized descriptively by treatment, IBS subtype and time period.

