2.3 Schedule of Activities

The complete schedule of study activities, often referred to as a “Time and Events” (T+E) table, is presented in [Table 1](#). Please observe the following when interpreting it:

- The **Phase 1 run-in period** will start the day after the **Baseline Visit**.
- The **Onboarding Call** will occur as soon as possible (at least 1 day but not more than 14 days) after the Phase 1 run-in period. The call will take place on the next mutually agreeable non-holiday weekday.
- Randomization occurs on the day of the Onboarding call, which we define as “Day 0” in our framework.
- **Phase 2 (treatment)** will begin no more than 7 days after the Onboarding call.
- As part of ensuring the above schedule of activities are completed in a timely manner and in accordance with the protocol, the study team shall utilize phone call, email, and text-based reminders sent to the study subjects.

Please refer to [Section 8](#) for a detailed description of assessments described in [Table 1](#).

	Online Screening	Baseline Visit	Run-In Period (weeks -4 to -1)	Onboarding Call day 0	Treatment Period (weeks 1-12)	Run-Out Period (weeks 13-16)	LTE 1: (weeks 35-38)	LTE 2: (weeks 61-64)
Informed Consent	X							
Diagnosis (Rome IV)		X						
Inclusion Exclusion Criteria		X						
Abdominal Pain Severity			Daily		Daily	Daily	Daily	Daily
Randomization				X				
Screening & Onboarding				X				
Treatment Adherence Data (Wistia)					Continuous import			
Stool Consistency			Daily		Daily	Daily	Daily	Daily
Stool Frequency			Daily		Daily	Daily	Daily	Daily
Adverse Event Reports			X	X	X	X	X	X
IBS QOL		X				Once at week 16	Once at week 38	Once at week 64
TIS		X						
WPAI		X			Once at week 8	Once at week 16	Once at week 38	Once at week 64
Concomitant medication assessment		X (checked)			Once at week 8	Once at week 16	Once at week 38	Once at week 64

		by physician)					
PHQ-4			X			Once at week 16	Once at week 38
Satisfaction Survey						Once at week 16	
Blinding assessment						Once at week 16	

Table 1 Schedule of Activities

Abbreviations: IBS QOL=Irritable Bowel Syndrome Quality of Life Questionnaire; LTE=long-term extension; PHQ-4=Patient Health Questionnaire-4; TIS=North Carolina Thought Impact Scale; WPAI =Workplace Productivity and Activity Impairment Questionnaire.

Participants are asked to complete their Baseline Surveys within 7 days of enrollment, which include IBS QOL, PHQ4, TIS, and WPAI.

TABLE OF CONTENTS

1	ADMINISTRATIVE INFORMATION												

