6.2 Inclusion Criteria

To be eligible to participate in this study, an individual must meet all of the following criteria, which are assessed at the Baseline Screening event (see previous section):

1. Provision of signed and dated informed consent form
2. Stated willingness to comply with all study procedures and availability for the duration of the study
3. Male or female, aged 18-70
4. Confirmation of the IBS and IBS subtype diagnosis by a study physician using Rome IV diagnostic criteria (see [Appendix A](#))
5. Possess an iOS or Android smartphone or an iOS tablet (iPad) released in 2015 or later.
6. Agreement to input information about their abdominal pain and bowel movements on a daily basis into Curebase software
7. Agreement to have their anonymized data stored in the cloud for up to 2 years after the conclusion of the study, and to have the data used for research purposes.

8. Agreement to maintain stable dosage of IBS medications during the course of treatment and not to add new IBS medication or stop current IBS medications unless directed to do so by the subjects treating physician. Changes in treatment will be captured using a concomitant medication assessment.

At the **Day 0 Screening** event, subjects must also meet the following criteria:

1. Average “Worst Daily Pain Severity” of ≥ 3 on an 11-point NRS over the full 28-day symptom tracking period
2. Consistent submission of Pain Severity scores via the Curebase app (data submitted on 70% or more of days in the symptom tracking window)

This study attempts to achieve excellent representation of women and minorities in the enrolled population, and there are no restrictions on eligibility based on the subject’s sex, gender, or race. Please see [Section 5.5](#) for information about how women and minorities will be recruited into the study.

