8.6.5 Adverse Event and Serious Adverse Event Reporting

The occurrence of AEs, SAEs, and Protocol Deviations (PDs) shall be reported through a unidirectional, HIPAA-compliant, web-based communication channel. Event reports may be initiated at any time by the subject or the investigator. All logging of event reports shall be retained for the duration of the study to provide proper documentation in accordance with FDA and ICH GCP requirements. The adverse event will be triaged based on subject content and urgency.

In the event of an AE, SAE, or PD, the message will be immediately sent to the Curebase team for determination of severity and relatedness to the investigational treatment. The study team will

collect information from the subject as necessary and create a final event report for logging within a specified timeframe. Reports containing AEs will be processed and documented.

Reports containing SAEs shall be completed and filed per regulatory requirements. The information in a SAE report should be completed as fully as possible and contain at a minimum:

- Subject ID number
- Start date of the event
- Description of the event
- Study physician's name
- Investigator causality assessment
- Investigator seriousness assessment

If safety information not available at the time of the first report becomes available at a later date, the study team member should submit follow-up safety information to Curebase. All SAEs should be followed up until resolution or permanent outcome of the event. The timelines and procedure for follow-up reports are the same as those for the initial report. Detailed study reporting procedures shall be standardized as documented in a formal Safety Monitoring Plan.

9 Statistical Considerations

A Statistical Analysis Plan (SAP) will be prepared and finalized before unblinding of subjects' treatment assignment. This document will provide further details regarding the definition of analysis variables and analysis methodology to address all study objectives. A blinded data review will be conducted before unblinding of subject's treatment assignment. This review will assess the accuracy and completeness of the study database, subject evaluability, and appropriateness of the planned statistical methods.

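### The IBS-D/IBS-M stool-consistency responder is defined on a raw count of loose-stool days with no denominator, so the bar for response moves with diary completeness

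*Combined protocol and SAP*

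**What the plan says.** Section 9.4.3.3 (Stool Consistency) defines response for IBS-D and IBS-M subjects as a "greater than or equal to 50% reduction from baseline (Phase 1) in the number of days with a BSFS score of 6 or 7". It then sends the analysis to the primary-endpoint methods, so this is a planned between-arm test. (It cites section 10.4.2; the primary analysis is in 9.4.2.)

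Related text:

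- **Percentages elsewhere in 9.4.3.3.** The MMRM uses the percentage of days in the normal BSFS group, and the descriptive summary also uses percentages.
- **Neighbouring endpoints.** Sections 9.4.3.2 (pain frequency) and 9.4.3.4 (stool frequency) both restrict the calculation to days with a recorded assessment. The responder sentence does not.
- **Completeness.** Section 9.4.1 says "at least 50% of the required assessments must be collected to be able to derive the average daily abdominal pain intensity and like endpoints". Whether this responder is a like endpoint is not stated. Section 6.2 requires, for Day 0 eligibility, "data submitted on 70% or more of days in the symptom tracking window", but for pain scores only.
- **Missing data.** Section 9.4.1 plans one analysis with no replacement and one in which "Missing values at post-baseline assessments will be imputed using the multiple imputation method". It does not say whether imputation is by day or by period.
- **Deferral.** The Synopsis says "Stool consistency response will be analyzed with methods similar to those used to assess the primary endpoint, as described in the Statistical Analysis Plan". Section 9 says of the SAP: "This document will provide further details regarding the definition of analysis variables and analysis methodology to address all study objectives". No separate SAP text is among the documents.

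**The concern.** A count of loose-stool days falls for two reasons: the subject improves, or the subject records fewer days. The rule as written cannot tell them apart. A subject with 14 loose days out of 28 in Phase 1 and 7 out of 14 in Phase 3 is a responder, although the rate is 50% both times. A subject with a sparse Phase 1 diary and a full Phase 3 diary faces a harder test than the nominal 50%.

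At stake are the meaning of the response rate in each arm and, if Phase 3 completeness differs by arm, the validity of the between-arm test. Phase 1 ends before allocation ("Randomization occurs on the day of the Onboarding call", section 2.3), so missing Phase 1 days add misclassification but no systematic difference between arms. Only Phase 3 completeness can do that.

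**Working it through.** **Stated figures.** The plan gives no rate, power or error figure for this responder. Its only power statement (section 9.2: 300 completers, 26% against 44%, 5% level) concerns the primary endpoint. It reproduces, with power 0.909 at 150 per arm, and has no bearing here.

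**Step 1: the threshold (no assumptions).** Let c1, c3 be the BSFS 6-7 days and n1, n3 the recorded days in Phases 1 and 3. The rule is c3 ≤ 0.5 × c1. Dividing by recorded days, (c3/n3)/(c1/n1) ≤ 0.5 × n1/n3. The fall in the observed share of recorded days needed to respond is therefore 1 - 0.5 × n1/n3.

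Each phase has 28 days. The 70% rule gives 0.70 × 28 = 19.6, so 20 days; applying it to stool entries is an assumption, because it covers pain scores. The 50% rule gives 14 days, if it applies to this endpoint.

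| Phase 1 days | Phase 3: 28 | 24 | 20 | 14 |
|---|---|---|---|---|
| 28 | 50% | 42% | 30% | 0% |
| 24 | 57% | 50% | 40% | 14% |
| 20 | 64% | 58% | 50% | 29% |

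For example, 1 - 0.5 × 28/20 = 0.30 and 1 - 0.5 × 20/28 = 0.643. With equal recorded days the answer is always 50%.

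**Step 2: misclassification (illustration).** The documents give no loose-day rates. Assume a 40% mean rate, subject rates from a Beta distribution with concentration 8, binomial counts, at least one loose day in Phase 1, and no true change. Proportion called responders:

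| Phase 1 / Phase 3 days | Count rule | Percentage rule |
|---|---|---|
| 28 / 28 | 6% | 6% |
| 28 / 24 | 11% | 6% |
| 28 / 20 | 21% | 7% |
| 20 / 28 | 2.5% | 5.5% |

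The error goes both ways. At 28/20 days, over concentrations 4 to 20, the count rule gives 20-22% and the percentage rule 6-9%.

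**Step 3: between-arm test (illustration).** Assume 95 IBS-D/IBS-M completers per arm. The section 7.2.2 targets of at least about 25% for each of the three main subtypes imply roughly 50-75% of 150, or 75-112. Also assume 26 Phase 1 days, Phase 3 days binomial out of 28 with a floor of 14, the step 2 rates, no true effect, and a two-sided 5% test. The last column also requires an observed difference of at least 10 points.

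| Phase 3 completeness, arm A / arm B | Count rule rejects | Count rule with 10-point criterion |
|---|---|---|
| 80% / 80% | 5% | 3% |
| 85% / 90% | 8% | 2% |
| 80% / 90% | about 20% | 11% |

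A CMH test over gender by subtype gives 5%, 8% and 19% without the criterion. Over loose-day rates of 25-60% and concentrations 4-20, the rejection rate without the criterion is 5-9% at 85/90 and 13-23% at 80/90. The percentage rule never exceeded 6.5% in any case run. At 80/80 the count rule labels 12% of unchanged subjects as responders, against 6% for the percentage rule.

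**Step 4: do the planned safeguards correct it?** The 50% rule bounds n3 but does not rescale the count. The no-replacement analysis leaves it as it is. Day-level imputation would repair Phase 3: filling it to 28 days brings rejection to 4-5%. It covers post-baseline values only, so a short Phase 1 diary still matters: null responders are 2.5% at 20 Phase 1 days and 5.7% at 28.

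**The case against.** **The SAP may settle it.** The Synopsis and section 9 hand variable definitions to the SAP, and a scaling rule there cannot be excluded. This stands as a limit: what is shown is a fault in the protocol wording. If such a rule exists, the protocol sentence disagrees with it and needs alignment.

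**A percentage was probably meant.** The surrounding text points that way, and section 9.4.3.3 is loosely drafted: even its percentages have no stated denominator (28 days, recorded days or BSFS-scored days). That is plausible, but a programmer following the responder sentence would compute a raw count.

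**Extreme incompleteness is unlikely.** Section 6.5 withholds payment below 5 of 7 weekly pain surveys (5 × 4 = 20 of 28 days), and section 8.3 has missed entries chased. Both make the 14-day case less likely without excluding it. They concern pain surveys or data entry generally, and a subject at 20 Phase 3 days after a full Phase 1 still faces a 30% bar.

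**No arm gap is documented.** Reminders, payment and ePRO are common to both arms, and subjects are blinded to the hypothesis. This stands. A reader might infer that the test of this endpoint will have inflated type I error; the documents do not support that, because inflation needs a Phase 3 gap that nothing in them predicts. Moreover, if the primary rule that "the magnitude of the difference in pooled proportions is at least 10 percentage points" carries over, which is not stated, the 85/90 case falls below 5%.

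**Conclusion.** The definition is wrong as written, in one between-arm analysis of a secondary endpoint. The moving threshold, from 0% to 64% over 20-28 Phase 1 days and 14-28 Phase 3 days, is arithmetic; only the choice of those limits involves an assumption. All response and rejection rates rest on assumed loose-day rates, between-subject spread, completeness and arm size, and are illustrations.

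Three further inferences are tempting and fail:

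- The threshold is not a required fall in the true rate. It applies to the observed share; even at 28/28 days some unchanged subjects respond by chance.
- The rule does not always add false responders. It removes responders when Phase 3 is the more complete phase.
- The primary endpoint is not affected, because it is an average of daily scores.

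With equal completeness in the two arms the result is misclassification, with type I error near 5%. With unequal Phase 3 completeness the comparison is biased toward the arm with less complete diaries, by an amount that the documents do not allow anyone to predict.

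**What to change.** Before unblinding, amend section 9.4.3.3:

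1. Define response as a reduction of 50% or more from Phase 1 in the percentage of recorded diary days with BSFS 6 or 7.
2. Apply the 50% completeness rule of section 9.4.1 to this endpoint in both phases, on stool entries.
3. State how a recorded day without a bowel movement counts, since section 8.4.3 has BSFS scored only when there is a movement. A reasonable choice is to keep it in the denominator as a day without BSFS 6-7. Use the same denominator for the percentage-of-days MMRM and summaries.
4. If the SAP already has a scaling rule, align the protocol sentence with it.
5. Correct the cross-reference to section 9.4.2, and say whether the 10-point criterion applies here.

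The cost is a short rewrite of one secondary definition. Daily bowel-movement counts and BSFS are already collected, so no new data are needed. Timing matters, because choosing the denominator after unblinding would be open to the charge of being driven by the data.
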